14.2 Meetings

We will utilize the Data and Safety Monitoring Plan of the Dan L. Duncan Cancer Center at Baylor College of Medicine (DLDCC-BCM). Additionally, the Principal Investigator will review all adverse events as they occur to evaluate causality and severity. This will ensure that any unanticipated risks or changes to the risk/benefit ratio are identified and reported in a timely manner.

The external Data and Safety Monitoring Board (DSMB) at DLDCC-BCM will review the study annually, at a minimum. The DSMB consists of five members not affiliated with BCM or the DLDCC, who have prior experience and expertise in the conduct of clinical trials. The DSMB will review and monitor study progress, toxicity, safety and other data from this study.

Information that raises any questions about participant safety or protocol performance will be addressed by the Principal Investigator, statistician and study team. Should any major concerns arise, the DSMB will offer recommendations regarding whether or not to suspend the study.

Information to be provided to the DSMB includes, but is not limited to, the following: participant accrual, participant demographics, response data, and toxicity data. Additional information may be provided to the DSMB upon request. Additional information regarding DSMB policies and procedures is located in the DLDCC External DSMB Charter.

15. REGULATORY CONSIDERATIONS

15.1 Informed Consent

The investigator (or designee) will explain to each participant the nature of the study, its purpose, the procedures involved, the expected duration, the potential risks and benefits involved and any discomfort it may entail. Each participant will be informed that participation in the study is voluntary, that s/he may withdraw from the study at any time, and that withdrawal of consent will not affect his/her subsequent medical treatment or relationship with the treating physician(s) or institution. The informed consent will be given by means of a standard written statement, written in non-technical language, which will be IRB-approved. The participant should read and consider the statement before signing and dating it, and will be given a copy of the document. No participant will enter the study or have study-specific procedures done before his/her informed consent has been obtained.

In accordance with the Health Information Portability and Accountability Act (HIPAA), the written informed consent document (or a separate document to be given in conjunction with the consent document) will include a subject authorization to release medical information to the study sponsor and supporting agencies and/or allow these bodies, a regulatory authority, or Institutional Review Board access to subjects' medical information that includes all hospital records relevant to the study, including participants' medical history.

15.2 Ethics and GCP

This study will be carried out in compliance with the protocol and Good Clinical Practice, as described in:

ICH Harmonized Tripartite Guidelines for Good Clinical Practice 1996.

US 21 Code of Federal Regulations dealing with clinical studies (including parts 50 and 56 concerning informed consent and IRB regulations).

Declaration of Helsinki, concerning medical research in humans (Recommendations Guiding Physicians in Biomedical Research Involving Human Subjects, Helsinki 1964, amended Tokyo 1975, Venice 1983, Hong Kong 1989, Somerset West 1996).

The investigator agrees to adhere to the instructions and procedures described in it and thereby to adhere to the principles of Good Clinical Practice that it conforms to.

15.3 Compliance with Trial Registration and Results Posting Requirements

Under the terms of the Food and Drug Administration Modernization Act (FDAMA) and the Food and Drug Administration Amendments Act (FDAAA), the Principal Investigator is solely responsible for determining whether the trial and its results are subject to the requirements for submission to the Clinical Trials Data Bank, <http://www.clinicaltrials.gov>. Information posted will allow participants to identify potentially appropriate trials for their disease conditions and pursue participation by calling a central contact number for further information on appropriate trial locations and study site contact information.

16. STATISTICAL CONSIDERATIONS

16.1 Study Design

This phase 2 biomarker-stratified study employs a modified optimal Simon two stage design. The decision rule, based on an adaptation of the approach of Jones and Holgren[1], is detailed below.

The primary endpoint is PFS24, where the success is defined as being alive and progression-free at 24 weeks after initiation of study treatment.

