7.2 Treatment Phase

Once registered/enrolled, participants will start treatment with sitravatinib 100 mg once daily until disease progression (assessed by RECIST 1.1), unacceptable toxicity, death or discontinuation from treatment for any other reason. Each cycle is 28 days in length. Study assessments, and efficacy and safety monitoring will continue as outlined in the study calendar.

All assessments must be performed prior to the administration of study treatment unless otherwise specified. The following windows apply:

- On-study assessments for all cycles must be performed within +/- 3 days of Day 1, unless otherwise indicated.
- Re-staging scans for tumor evaluations should continue on schedule if treatment is held or delayed.

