8. STUDY CALENDAR

Test/Procedure	Pre-Study ¹	C1D1	C1D14	Subsequent Cycles Day 1	End of Treatment	Safety Follow-Up ¹¹	Survival Follow-Up
Informed Consent	X						
Participant Demographics	X						
CLINICAL EVALUATIONS							
History and Physical Exam	X	X	X	X	X		
Height	X						
Vital signs and weight	X	X	X	X	X		
Performance Status	X	X	X	X	X		
LABORATORY/RADIOLOGIC EVALUATIONS							
CBC/differential	X		X	X	X		
Comprehensive Metabolic Panel	X		X	X	X		
TSH	X		X	^{X⁴} (odd cycles)	X		
Urine Protein/Creatinine Ratio	X		X	^{X⁴} (odd cycles)	X		
Pregnancy test	^{X²}						
Tumor Assessments	X			^{X⁵}	X		
Echocardiogram	X			^{X⁶}			
TREATMENT DISPENSATION							
Sitravatinib		X		X			
CORRELATIVE							
ctDNA collection	X		X	^{X⁷}	X		
CTC collection	X		X	^{X⁷}	X		
Tumor/Tissue Biopsy ⁸	^{X¹⁰}		^{X³}		X		
Archival tissue	^{X⁹}						
ADDITIONAL INFORMATION							
Concomitant Medications	X		X	X	X	X	
Adverse Events/Toxicity Assessment				X	X	X	
Compliance Assessment				X	X		
Assess vital status							^{X¹²}

NOTE: The schedule may be modified +/- 3 days due to scheduling delays or conflicts (e.g. holidays, inclement weather, vacations, etc.)

1. All pre-study assessments, with the exception of the informed consent, must be performed within 28 days prior to starting study treatment, unless otherwise indicated.
2. Urine or serum pregnancy test is acceptable; to be performed for women of child-bearing potential only
3. May be performed any time between Cycle 1, Day 14 and Cycle 3, Day 14
4. To be performed prior to dosing on C3D1, then prior to dosing on Day 1 of every odd-numbered cycle thereafter (e.g., C5D1, C7D1, etc.)
5. Clinical and radiological tumor assessments will be performed by CT, PET or MRI scan at baseline and then every 2 cycles (i.e., within 7 days prior to Cycles 3, 5, 7, and 9) until disease progression. The same testing modality should be used for each evaluation. Responses of CR or PR should be confirmed with a second assessment no earlier than 4 weeks, but no later than the next scheduled scan, per protocol. Brain MRI and bone scan should be performed if clinically indicated (e.g., participants with known history of bone or brain mets). Results must be reviewed for each scan prior to dosing at next cycle
6. To be performed within 7 days prior to C4D1. Further echocardiograms may be performed as clinically indicated.
7. To be collected on C2D1, C3D1, then on Day 1 of each odd-numbered cycle thereafter (e.g., C5D1, C7D1, etc.)

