12.4.6 Progression-Free Survival

Progression-free survival (PFS) is defined as the time from the initiation of the study treatment until the date of objective disease progression or death (by any cause in the absence of

progression).

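### Read literally, progression first seen on a pre-Cycle 7 scan done up to 3 days after week 24 counts as a PFS24 success; Section 16.1 should name the deciding scan

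*Combined protocol and SAP*

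**What the plan says.** - **Endpoint (16.1).** PFS24 is the primary endpoint, "where the success is defined as being alive and progression-free at 24 weeks after initiation of study treatment". No scan is named as deciding it, and no window is attached.
- **Dating (12.4.6).** PFS is "defined as the time from the initiation of the study treatment until the date of objective disease progression or death".
- **Cycle length (7.2).** "Each cycle is 28 days in length".
- **Scan schedule (Section 8, footnote 5).** Tumor assessments are due "every 2 cycles (i.e., within 7 days prior to Cycles 3, 5, 7, and 9) until disease progression".
- **Calendar allowance (Section 8, NOTE).** "The schedule may be modified +/- 3 days due to scheduling delays or conflicts". No row of the calendar is exempted.
- **Visit window (7.2).** "On-study assessments for all cycles must be performed within +/- 3 days of Day 1, unless otherwise indicated". This rule gives way to footnote 5, which sets its own window for scans. Section 7.2 also keeps restaging on schedule when treatment is held or delayed.
- **Decision rule (16.2) and error rates (16.3).** At least 1 success in 7 opens Stage 2. The final thresholds are 3 of 25 (combined path) and 2 of 15 (PTPN12 low path). The unacceptable rate is 3% and the one-tailed alpha is 0.075.

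**The concern.** The endpoint is fixed to a calendar date, while the scan that decides it may legitimately take place after that date. Consider a participant with no progression at the pre-Cycle 5 scan (about week 16) and progression on the pre-Cycle 7 scan. Scanned on day 166, this participant is a failure. Scanned on day 170, the same participant has a PFS time beyond day 168 and, on a literal reading of 12.4.6 with 16.1, is a success. Only the appointment has changed.

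The misclassification runs one way, towards success. With thresholds of 1 in 7, 2 in 15 and 3 in 25, one such participant can open Stage 2, pool the strata or turn the final verdict. Scans are read at the sites, with no independent review planned (12.4.7), so the scoring rule should be fixed before the data are seen.

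**Working it through.** Days are counted as elapsed from first dose.

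**1. Calendar.** Cycle 7 Day 1 is 6 × 28 = 168 days after Cycle 1 Day 1, and 24 × 7 = 168, so it coincides with week 24.
- Footnote 5 window: 168 − 7 = 161 to 168.
- With the NOTE: 161 − 3 = 158 to 168 + 3 = 171.

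An in-protocol scan can therefore fall on days 169 to 171. Sections 12.4, 16.1, 16.5.1 and 16.6 contain nothing that assigns such a scan to the week-24 time point.

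**2. The plan's own figures.** Write b(x; n, p) for the binomial probability.
- PTPN12 low path (at least 1 of 7, then at least 2 of 15): sum over x = 1 to 7 of b(x; 7, p) × P(Bin(8, p) ≥ 2 − x). At p = 0.30 this is 0.903 (stated 90%). At p = 0.03 it is 0.0549.
- Combined path (at least 1 of 7 in high/normal, then at least 3 of 25): sum over h = 1 to 7 of b(h; 7, p) × P(Bin(18, p) ≥ 3 − h). At p = 0.25 this is 0.852 (stated 85%). At p = 0.03 it is 0.0253.
- Whole design with both strata at 3%: 0.0253 + 0.97^7 × 0.0549 = 0.0253 + 0.8080 × 0.0549 = 0.0696.

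The power figures reproduce. The whole-design error of 7.0% lies under the stated 0.075, which fits a ceiling.

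**3. Size of the effect under the null.** Two inputs are assumptions, not in the documents: exponential PFS through 3% at week 24, and the share f of decisive scans done after day 168.
- S(t) = 0.03^(t/24), so S(16) = 0.0965.
- Progression first seen on the week-24 scan: 0.0965 − 0.0300 = 0.0665.
- Scored success rate: q = 0.03 + f × 0.0665, entered in the whole-design formula for both strata.

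| f | q | Whole-design false-success probability |
|---|---|---|
| 0 | 3.00% | 7.0% |
| 1% | 3.07% | 7.3% |
| 2% | 3.13% | 7.6% |
| 5% | 3.33% | 8.5% |
| 10% | 3.67% | 10.2% |

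The total reaches 0.075 at q = 3.119%, that is f = 0.00119 / 0.0665 = 1.8%.

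**4. Sensitivity to the week-16 rate.**

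| Week-16 PFS | f | q | False-success probability |
|---|---|---|---|
| 5% | 5% | 0.03 + 0.05 × 0.02 = 3.1% | 7.4% |
| 5% | 10% | 0.03 + 0.10 × 0.02 = 3.2% | 7.9% |
| 15% | 5% | 0.03 + 0.05 × 0.12 = 3.6% | 9.8% |
| 15% | 10% | 0.03 + 0.10 × 0.12 = 4.2% | 13.1% |

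**The case against.** **The plan already puts the scan before week 24.** Footnote 5 closes the window on day 168, the visit window in 7.2 yields to it, and dose holds do not move scans. Scan results must also be reviewed before the next cycle is dosed, so a late scan holds up Cycle 7. The NOTE is an exception for scheduling conflicts. This stands: late scans should be uncommon, and the gap is 3 days wide. It does not remove the gap, because the NOTE exempts no row.

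**Scoring as success is an inference.** Section 16.1 does not cite 12.4.6, and 16.5.1 speaks of progression-free status at 24 weeks. An analyst could sensibly read that as status at the week-24 restaging, which makes progression on that scan a failure. That reading is reasonable, but nothing written requires it.

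**The magnitude depends on assumed inputs.** This stands. The documents give neither f nor a PFS curve, and at week-16 PFS of 5% a late share of 5% stays within 0.075. The sum also treats the 3% as free of scan timing. Section 16.3 gives no source for it; if it was itself scored by scan date, part of the increase is counted twice.

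**Conclusion.** The gap is real and narrow. As written, an in-protocol pre-Cycle 7 scan on days 169 to 171 that first shows progression can be scored as a PFS24 success. On the assumptions above, the false-success probability rises from 7.0% to between 7.3% and 10.2% for late shares of 1% to 10%. At a 10% late share it is 7.9% to 13.1% if week-16 PFS is 5% to 15%. These are illustrations, not predictions.

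Three stronger readings are not supported:
- A reader might infer that the trial's type I error is substantially inflated. That needs a high late share, for which the documents give no basis, and the default window closes at week 24.
- A reader might infer that scans slipping well past week 24 have the same status. Beyond day 171 they are outside the written windows and are deviations.
- A reader might infer that the stated alpha or power is miscalculated. It is not: both power figures reproduce, and the design meets 0.075 when progression on the week-24 scan is always a failure.

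Correction is still warranted, because one participant can decide the outcome and the remedy is nearly free.

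**What to change.** In 16.1, name the pre-Cycle 7 (week-24) restaging, done within its permitted window including the 3-day allowance, as the PFS24 assessment. Suggested wording: *A participant is a PFS24 failure if death occurs by week 24, or if PD is documented at or before the pre-Cycle 7 restaging, whatever the exact date of that scan within its window.*

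In footnote 5, keep the 7-day window before Cycle 7 and state that it is counted from the nominal week-24 date, in line with 7.2. Re-anchoring scans to week numbers without a window should be avoided: with the 3-day allowance still in place, it could put more scans after week 24.

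A rule that counts PD on whatever scan comes first after week 24 should be left out or limited to a stated short window. Without a limit, PD first seen at week 32 after a missed week-24 scan would be a failure even for someone progression-free at week 24.

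Cost: a sentence or two in 16.1 and a footnote clarification, with no added scans or participants. The observed PFS24 rate may be slightly lower. The null rate stays at the 3% on which 16.3 rests, and the reproduced error and power figures are unchanged.

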16.2 Decision Rule(s)

The general flow and decision points are illustrated in Figure 4.

[figure not shown]

Figure 4. Adapted Phase 2 Design.

In Stage 1, the study will separately enroll seven PFS24 evaluable participants each in the PTPN12*high/normal* and PTPN12*low* cohorts. If there are no PFS24 events in the PTPN12*high/normal* cohort, enrollment to that stratum will close. If there is at least one PFS24 event observed in the PTPN12*high/normal* cohort, then, in Stage 2, the previously accrued PTPN12*low* and PTPN12*high/normal* cases will be combined into a single cohort, and the study will enroll additional cases, regardless of biomarker status, up to a total of 25 participants. At the end of the trial, three or more PFS24 events will be required to deem the therapy a success.

If there is no PFS24 event in the PTPN12*high/normal* cohort during Stage 1, the PTPN12*low* cohort will continue to accrue to 7 participants. If there are no PFS24 events in the PTPN12*low* cohort, enrollment to that stratum will close, and the trial will close. If there is at least one PFS24 event, then, in Stage 2, the study will accrue up to a total of 15 PFS24-evaluable PTPN12*low* participants. At the end of the trial, two or more PFS24 events will be required to deem the therapy a success, with PTPN12*low* status as a biomarker of benefit. Extensive simulations

indicate that operating characteristics of the proposed design perform as expected and are independent of the frequency of PTPN12*low* status.

16.3 Sample Size and Accrual Rate

Up to twenty-five PFS24-evaluable participants will be required. This study will have 90% power ($\alpha=0.075$ one-tailed) to detect a PFS24 rate of 30% in the PTPN12*low* cohort compared to an unacceptable rate of 3%, and 85% power to detect 25% vs 3% in the unselected group. The study is expected to complete accrual within 2 years of study initiation.

16.4 Stratification Factors

Participants will be enrolled into two cohorts based on Protein Tyrosine Phosphatase, Non-Receptor Type 12 (PTPN12) status, which will be determined via analysis of tissue from a metastatic site: PTPN12*low* or PTPN12*high/normal*.

16.5 Endpoints and Analysis

16.5.1 Primary Endpoint and Analysis

Progression-free survival status at 24 weeks will be used in trial decision-making as described above. At the end of the trial, PFS24 events will be summarized descriptively with counts, rates and 95% confidence intervals, with appropriate adjustment for the group sequential nature of the study design [23].

16.5.2 Secondary Endpoints and Analysis

Time to progression (TTP), objective response rate (ORR), and clinical benefit rate (CBR) will be summarized descriptively using appropriate statistics such as counts, rates, and Kaplan-Meier estimates for time to events and 95% confidence intervals.

The assessment of safety will be based on the frequency of adverse events, grade, attribution, and on the number of laboratory values that fall outside of pre-determined ranges. In particular, the number of participants experiencing grade 3 or higher adverse events will be summarized. Data will be summarized descriptively with counts, rates and 95% confidence intervals, as appropriate.

16.5.3 Exploratory Endpoints and Analysis

CTCs, CTC PTPN12 expression and ctDNA will be assessed longitudinally and will be correlated with baseline PTPN12 expression, to determine whether baseline CTCs can be used to assess PTPN12 status, to determine whether CTCs and ctDNA are predictive of response and/or PFS24. As appropriate, general linear mixed models will be used to model CTC and/or ctDNA trajectories. Exploratorily, phosphoproteomics will be examined before and after treatment to identify differentially expressed phosphoproteins due to treatment and baseline levels or changes in the phosphoproteome that might be predictive of clinical benefit. Tumor kinase profiling will be examined to identify differential kinase activity. Similarly, immune biomarkers will be examined to identify baseline differences or differential changes that might indicate the effect of immunocomponents on response. Data will be summarized descriptively with means and/or medians and 95% confidence intervals. False discovery methods will be employed to avoid multiple comparison issues with these higher dimensional data.

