3.3 Exploratory Objectives

- 3.3.1 To examine the relationship between Circulating Tumor Cell (CTC) expression of PTPN12 and tumor tissue expression to determine if CTC analysis can contribute to an assessment of PTPN12 status and response to treatment
- 3.3.2 To examine the relationship between acute changes in digital droplet PCR-based ctDNA mutant allele frequencies in the first month of treatment and subsequent radiological response evaluations
- 3.3.3 To evaluate the effect of sitravatinib on the drug bead-based tumor kinase profiling and mass spectrometry-based phosphoproteomics through examination of protein

extracts from tumor biopsy material before and during treatment, performed on OCT-embedded snap frozen tissue biopsy from patients with disease accessible by core needle biopsy

- 3.3.4 To evaluate immune biomarkers to explore the effects of sitravatinib on the immune microenvironment and the influence of tumor infiltrating lymphocytes on response

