4.2 Correlative Science Background

Orthogonal approaches have revealed that PTPN12 is recruited to inhibit several RTK receptors after ligand stimulation, thereby serving as a feedback mechanism to limit receptor signaling. Response to combination RTK inhibition is correlated with PTPN12 deficiency, suggesting that impaired receptor feedback may establish a combined addiction to these proto-oncogenic receptors. Cancer-associated mutation of PTPN12 or reduced PTPN12 protein levels diminish this feedback mechanism, leading to aberrant activity of these receptors. PTPN12 deficiency in TNBC is largely secondary to absent protein rather than mutation, and low PTPN12 levels have been reported in 62% of all TNBC. Inactivating PTPN12 mutations account for only 3% of PTPN12 deficiency.

A highly specific PTPN12 monoclonal antibody has been developed at Baylor College of Medicine for PTPN12 analysis. An immunohistochemistry (IHC) assay will be used to detect the level of this protein in primary and metastatic breast cancer tissue. This assay will be used to place patients into the two cohorts of the study. Additionally this antibody will be used to measure PTPN12 in CTCs by immunofluorescence to address whether CTC PTPN12 status will be a useful biomarker in future studies if the CTC status correlates well with tissue PTPN12 status. RTK signaling in cancer cells contributes to shape the immune microenvironment by regulating tumor secretomes. In addition we will collaborate with the Clinical Proteomic Tumor Analysis Consortium to analyze any OCT-embedded frozen specimens that are generated in the

protocol. We will analyze them using mass-spectrometry-based proteomics and also conduct RNA sequencing and Whole Exome Sequencing for a full proteogenomic profile [8]. We have recently adapted these techniques to interrogate fresh frozen core biopsy material embedded in OCT [9].

Recent data indicate that sitravatinib may impair myeloid-derived suppressor cells (MDSCs) and other immunosuppressive compartments, thus raising the provocative hypothesis that Sitravatinib may have both tumor-autonomous and non-autonomous immunostimulatory effects. Prompted by this knowledge, we will assess important constituents of the tumor immune microenvironment using established assays, and correlate the results to PTPN12 status.

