11.3.2 Analysis of Tissue Samples

11.3.2.1 PTPN12 IHC Assay

We will deploy the PTPN12 IHC on all formalin-fixed tissue accrued from the participants during the execution of the trial to identify changes in expression from primary to metastatic

disease, as a role of PTPN12 loss during metastatic progression has not been evaluated. If the PTPN12 status of the primary and metastatic samples are closely matched, analysis of the primary sample can be used for eligibility in future studies. For participants with accessible disease, pre-treatment, during treatment, and progression biopsies will be requested to profile the kinome in response to treatment using the drug bead technology. Upon completion of these studies we will understand whether primary tumor or CTC PTPN12 status, as opposed to a metastatic biopsy, can be used to determine eligibility in future studies.

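### Correlation (16.5.3) does not show whether CTCs assign patients to the same PTPN12 cohort as metastatic tissue, and 11.3.2.1 promises a firmer answer than the class sizes support

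*Combined protocol and SAP*

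**What the plan says.** - Section 16.5.3 (exploratory analysis): CTCs, CTC PTPN12 expression and ctDNA "will be correlated with baseline PTPN12 expression, to determine whether baseline CTCs can be used to assess PTPN12 status". It names no agreement measure, CTC cut-off or success threshold, and it does not mention primary tissue.
- Section 4.2 (correlative background): CTC PTPN12 status "will be a useful biomarker in future studies if the CTC status correlates well with tissue PTPN12 status". No number is attached.
- Section 3.3.1 (exploratory objective): the aim is to "determine if CTC analysis can contribute to an assessment of PTPN12 status".
- Section 11.3.2.1 on primary tissue: "If the PTPN12 status of the primary and metastatic samples are closely matched, analysis of the primary sample can be used for eligibility" in later studies. No statistic defines the match.
- Section 11.3.2.1, closing sentence: "Upon completion of these studies we will understand whether primary tumor or CTC PTPN12 status, as opposed to a metastatic biopsy, can be used" to set eligibility in future studies.
- Sections 4.2 and 16.4: status is a two-way label (low or high/normal), read by IHC, with metastatic-site tissue as the basis for cohort assignment. Section 11.3.1.1 reads CTCs by immunofluorescence.

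**The concern.** Replacing a metastatic biopsy with a blood sample is a classification problem. A later trial would need to know how often CTCs put a tissue-low patient in the low cohort, and how often they put a tissue-high/normal patient in the high/normal cohort. A correlation between two expression scales gives neither rate. It summarises how the values move together, and it can look strong while one class is classified poorly.

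Two further gaps bear on the same question. A patient in whom no CTC is found has no CTC expression value to correlate, and 16.5.3 gives no rule for such patients, although for a substitute test they are unclassified. The primary-versus-metastatic question has no analysis in 16.5.3 at all.

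At stake is what is concluded afterwards. A respectable correlation from this trial could be cited, under the closing sentence of 11.3.2.1, as grounds for dropping the metastatic biopsy in a later trial, without an estimate of the misclassification that would follow.

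**Working it through.** **1. What the sample size was built for.** The only sizing in the plan is for PFS24 (16.3), and it reproduces with the rules of 16.2.
- Low cohort: continue with at least 1 success in 7, then require at least 2 in 15. Exact power at a 30% rate is 90.3% (stated 90%).
- Pooled route: at least 1 in 7 high/normal, then at least 3 in 25. Exact power at 25% is 85.3% (stated 85%).

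No figure is given for the specimen comparison, so its precision is whatever these numbers leave.

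**2. Pairs per tissue class (16.2), taking one evaluable pair per PFS24-evaluable participant.**
- Low-only route: 15 low and 7 high/normal, 22 in all.
- Pooled route: 14 from Stage 1 plus 25 − 14 = 11 unselected. With 62% low among those 11 (the TNBC figure in 4.2), 0.62 × 11 ≈ 7, giving about 14 low and 11 high/normal.
- Both strata stop: 7 and 7.

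**3. Best case: every pair agrees.** The exact (Clopper-Pearson) two-sided 95% lower limit for n out of n is 0.025^(1/n).

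| Pairs, all agreeing | Where it arises | Lower limit |
|---|---|---|
| 7/7 | high/normal, low-only route | 59.0% |
| 11/11 | high/normal, pooled route (approx.) | 71.5% |
| 14/14 | low, pooled route (approx.) | 76.8% |
| 15/15 | low, low-only route | 78.2% |
| 22/22 | overall, low-only route | 84.6% |
| 25/25 | overall, pooled route | 86.3% |

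In the low-only route, perfect data would therefore still be compatible with misclassifying up to 100 − 59 = 41% of high/normal and 100 − 78 = 22% of low patients. One discordant pair in 25 lowers the overall limit to 79.7%, and two lower it to 74.0%.

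**4. Perfect pairs needed for a given lower limit t.** n = ln(0.025)/ln(t), rounded up: 17 for 80%, 23 for 85%, 36 for 90%.

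**5. What a correlation implies for classification.** Assumptions, for illustration only: the two scales are bivariate normal and each is cut at its own 62nd percentile, so there is no offset between cut-offs. With c = Φ⁻¹(0.62) and p = P(both below c), agreement is p/0.62 in tissue-low, (1 − 1.24 + p)/0.38 in tissue-high/normal, and p + (1 − 1.24 + p) overall. At r = 0.80, p ≈ 0.5225, giving 0.5225/0.62 = 84%, 0.2825/0.38 = 74% and 0.5225 + 0.2825 = 80.5%.

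| r | Agreement, tissue-low | Agreement, tissue-high/normal | Overall | Kappa |
|---|---|---|---|---|
| 0.396 (smallest significant at n = 25, two-sided 5%) | 72% | 54% | 65% | 0.25 |
| 0.70 | 81% | 68% | 76% | 0.49 |
| 0.80 | 84% | 74% | 80.5% | 0.59 |
| 0.90 | 89% | 82% | 86% | 0.71 |

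An observed r of 0.80 at n = 25 has a 95% interval of 0.59 to 0.91.

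**The case against.** The strongest reply is that this is exploratory work. Section 3.3.1 asks only whether CTCs can contribute, 11.3.1.1 calls the comparison exploratory, and cohort assignment in this trial rests on metastatic-site tissue. All of that stands, and it makes the point minor. It does not make correlation answer a substitution question, and it does not cover the closing sentence of 11.3.2.1, which carries no such qualification.

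A second reply is that 16.5.3 names no coefficient and 4.2 speaks of status correlating with status, so a cross-tabulation would fit the wording. That is a fair reading of 4.2. Section 16.5.3, however, refers to expression. If a cross-tabulation is meant, the statistic and the CTC cut-off are still missing, and the remedy is the same.

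A reader might also infer stronger faults that the documents do not support:
- *Primary tissue is to be validated by correlation.* It is not. Section 11.3.2.1 asks whether statuses match closely, and the gap is that no statistic is given.
- *A shift in the CTC scale would wreck agreement while the correlation stays high.* With r = 0.80 and a 0.5 SD shift, high/normal agreement falls from 74% to 48%. This requires one cut-off shared by IHC and immunofluorescence, which the documents do not state. The same shift raises tissue-low agreement from 84% to 96%, so overall agreement moves only from 80.4% (0.62 × 0.843 + 0.38 × 0.741) to 77.7% (0.62 × 0.957 + 0.38 × 0.482).
- *The sample cannot answer even with perfect agreement.* The plan sets no threshold. A result of 25/25 would clear a bar of 80% or 85% overall, though not 90%, and clearly poor agreement would be an answer too.
- *Patients without CTCs are to be dropped.* No such rule is written, and 11.3.1.1 tracks CTC number. The treatment of these patients is simply unspecified.

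**Conclusion.** The point holds in a limited form. For CTCs, the named method does not estimate the quantity the question needs, which is agreement with metastatic tissue within each PTPN12 class. For primary tissue, no statistic is stated. The closing sentence of 11.3.2.1 is firmer than the class-specific data can support: in the low-only route the best attainable lower limits are 59% for high/normal and 78% for low, and about 72% and 77% in the pooled route. Overall agreement could be bounded at 86% at best with 25 pairs.

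These limits assume one evaluable pair per PFS24-evaluable participant. The true count could be lower, because primary tissue is optional (11.2) and some patients may have no evaluable CTC. It could also be somewhat higher, because replaced participants (16.6) may also have baseline blood and tissue. The correlation-to-agreement figures rest on the bivariate-normal assumption and the 62% prevalence, and serve only as illustration.

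Severity is minor: the objective is exploratory, and no eligibility, safety or primary-endpoint decision in this trial turns on it.

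**What to change.** In 16.5.3:
- Set a low versus high/normal cut-off on the CTC scale before CTC results are compared with tissue.
- Report a paired 2x2 table of CTC status against metastatic tissue status, with percent agreement within tissue-low and within tissue-high/normal and exact 95% confidence intervals. Within-class agreement does not depend on how the cohorts were filled (7 and 7, then low-only in one route).
- Report participants with a blood sample but no evaluable CTC as not classifiable, and show that fraction.
- Use the same table for primary against metastatic tissue among participants with a primary block. Report block availability separately, since a missing block is not a failure of the test.
- Keep correlation as a supporting plot.

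In 11.3.2.1, restate the closing sentence as hypothesis-generating for later trials.

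The cost is a short edit to the two sections, the work of choosing a CTC cut-off, and a little more analysis. No new samples are needed. The downside is a less favourable stated conclusion.
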